Erythroid response is defined in those who with a pretreatment hemoglobin of < 9.0 g/dL as an increase in hemoglobin concentration of ≥ 1.5 g/dL above baseline without transfusion, or reduction in the transfusion unit by at least 4 units for 8 consecutive weeks compared with the pretreatment transfusion requirement in the previous 8 weeks prior to the first administration of AMG531 (Day -55 to Day 1).

Neutrophil Response

Neutrophil response is defined in those with a pretreatment absolute neutrophil count (ANC) of $< 0.5 \times 10^9/L$ as a 100% increase over the baseline, or an increase in ANC of $> 0.5 \times 10^9/L$ in subjects with a pretreatment ANC of $< 1.0 \times 10^9/L$.

Baseline

Baseline values are defined as the values obtained before dosing AMG531 on Study Day 1. Data obtained during the screening period will serve as baseline values for those not measured or reported on Study Day 1. If multiple evaluations are performed during the screening period for a particular test, with the exception of platelet count, the values measured closest to the first administration of AMG531 will be considered as the baseline values (if hemoglobin concentration at Study Day 1 is within 28 days after RBC transfusion, hemoglobin concentration determined during the screening period will be used as baseline hemoglobin).

Baseline Platelet Count

Baseline platelet count is defined as the mean of two lowest platelet counts measured in 8 weeks prior to enrollment. Platelet count that is obtained within 7 days after platelet transfusion will not be used. The baseline platelet according to the definition of protocol Master Ver1.1 (The mean of two lowest platelet counts measured in 8 weeks prior to enrollment. Platelet count that is obtained within 3 days after platelet transfusion will not be used.) will be also collected .

Platelet Transfusion

Platelet transfusion given due to platelet count of $< 10 \times 10^9/L$ (prophylactic transfusion) or due to bleeding (therapeutic transfusion).

RBC Transfusion

RBC transfusion given due to the hemoglobin concentration of ≤ 9.0 g/dL or due to symptomatic anemia

Adverse Drug Reaction

Adverse events of which causal relationship to the investigational product cannot be ruled out (any events assessed to be other than “unlikely” or “not related”).

Study Duration

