6.2.3 Recording concomitant medication and therapy in electronic Case Report Form (eCRF)

All concomitant medication and therapy that a subject received during the period after enrollment through to the end of the study will be recorded on electronic case report form (eCRF) by the investigator with the following information for each concomitant medication and therapy: name of drug, route of administration, duration of treatment and justification for the administration. Agents not intended for medical treatment such as rehydration including saline solution, dissolving solution, or contrast medium for imaging diagnostics are not required to be recorded.

Platelet transfusions given between the period within 56 days (Day -55) prior to the first administration of AMG531 (Day 1) and RBC transfusion given between the period of within 26 weeks (Day -181) prior to the first administration of AMG531 (Day 1) through to the end of study will be recorded in eCRF, including date of each transfusion, volume of transfusion (unit and mL), platelet count or hemoglobin concentration before each transfusion, and reason for each transfusion.

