8.2 Observations/assessments/examinations and schedule

8.2.1 Screening examinations

A signed and dated IRB approved informed consent must be obtained before any study specific procedures are performed. Procedures that are part of routine care are not considered as study specific procedures.

The screening period begins on the date of subject signed the IRB approved informed consent and continues until the date of first administration of AMG531. The following screening examination will be conducted within 4 weeks prior to the first administration of AMG531 (Week -4 to Day 1). Retesting during this period may be performed as needed.

Subjects who fail screening will be allowed to be re-screened if a remediable cause for the original screen failure is found.

- 1) Baseline characteristics: date on which the subject is diagnosed with AA, severity of AA (Appendix 2), previous treatments for AA (duration and sort of treatment), baseline platelet count, platelet transfusion in the previous 8 weeks prior to the first administration of AMG531 (Day -55 to Day 1), RBC transfusion in the previous 26 weeks prior to the first administration of AMG531 (Day -181 to Day1), concomitant medications, medical history, current complications, date of birth, gender, weight, and height, baseline platelet count according to the protocol Master Ver1.1 (The mean of two lowest platelet counts measured in 8 weeks prior to enrollment. Platelet count that is obtained within 3 days after platelet transfusion will not be used)
- 2) Bone marrow biopsy and aspiration with cytogenetics (M/E ratio, cellularity of bone marrow, reticulin grade (reticulin stain/trichrome stain (Appendix 1)), iron stain, narrative pathology report, cytogenetic report and exploratory test described in section 3.3.4)
- 3) Pregnancy test (excluding male subjects and female subjects underwent oophorectomy or hysterectomy or those who are non-childbearing potential i.e., menstrual periods have been absent for at least 12 months)
- 4) ECOG PS

- 5) Vital signs (systolic blood pressure, diastolic blood pressure and pulse rate)
- 6) Hematology (WBC, RBC, Hb, Ht, MCV, MCH, MCHC, PLT, Ret and WBC with differential count)
- 7) Serum chemistry (TP, ALB, T-Bil, D-Bil, AST, ALT, ALP, LDH, γ -GTP, T-Cho, UA, BUN, Cr, Na, K, Ca, P and Cl)
- 8) Blood iron-related parameters (Fe, TIBC, UIBC, TSAT and ferritin)
- 9) Blood coagulation and fibrinolysis (PT-INR, APTT and D-dimer)
- 10) Folic acid and vitamin B₁₂

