12.1.1 Efficacy

Platelet count measured within 7 days after platelet transfusion will not be subjected to the efficacy assessment. Likewise, hemoglobin concentrations determined within 28 days after RBC transfusion will not be subjected to the efficacy assessment. Neutrophil counts determined within 7 days of G-CSF as a rescue medication will not be used for the efficacy assessment.

Platelet count, hemoglobin concentrations and neutrophil counts determined in occasions other than in the scheduled visit in this study, including ordinary medical examinations and follow-up, will not be used for efficacy assessment.

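### The substitute baseline hemoglobin carries no transfusion-free condition, so it can be a value the plan's own 28-day rule rejects; erythroid and tri-lineage results can be biased, with net direction and size unknown

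*Combined protocol and SAP*

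**What the plan says.** The Baseline entry in the Definition of Terms normally takes the pre-dose value on Study Day 1. For hemoglobin it adds an exception: "if hemoglobin concentration at Study Day 1 is within 28 days after RBC transfusion, hemoglobin concentration determined during the screening period will be used" as the baseline. Nothing is said about how long after a transfusion that screening value must lie. For tests measured several times in screening, platelet count apart, the same entry says that "the values measured closest to the first administration of AMG531 will be considered as the baseline values". The platelet baseline, by contrast, has its own 7-day exclusion after platelet transfusion.

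Section 8.2.1 sets the timing: "The following screening examination will be conducted within 4 weeks prior to the first administration of AMG531 (Week -4 to Day 1"). It also says: "The screening period begins on the date of subject signed the IRB approved informed consent and continues until the date of first administration of AMG531".

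Section 12.1.1 states that "hemoglobin concentrations determined within 28 days after RBC transfusion will not be subjected to the efficacy assessment", and bars values obtained outside scheduled visits. It does not say whether either rule reaches the baseline value.

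The Definition of Terms opens the endpoint with an entry condition: "Erythroid response is defined in those who with a pretreatment hemoglobin of < 9.0 g/dL". One route to response is "an increase in hemoglobin concentration of ≥ 1.5 g/dL above baseline without transfusion". The other is a reduction of at least 4 units over 8 weeks against the 8 weeks before first dose. Section 12.1.1.2 restates both routes without the 9.0 g/dL condition. Tri-lineage response requires erythroid response. Section 12.4 leaves missing hemoglobin unimputed. Section 6.2.3 records RBC transfusions from 26 weeks before first dose, with dates and the "platelet count or hemoglobin concentration before each transfusion".

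**The concern.** The exception exists to keep transfused hemoglobin out of the baseline, but it draws the replacement from a period as long as the exclusion window and sets no condition on it. A screening sample taken after the transfusion that disqualified Day 1 is necessarily also within 28 days of that transfusion. A sample taken before it is clean only if no earlier transfusion fell in the preceding 28 days.

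The baseline enters two decisions. It is the reference for the 1.5 g/dL rise, so a raised baseline can hide a real improvement. If it also serves as the pretreatment value for the 9.0 g/dL condition, it can decide whether the subject is evaluable at all. Tri-lineage response and the summaries of hemoglobin change use the same value. On-treatment hemoglobin is explicitly cleaned of transfusion effect and the substitute baseline is not, so the two sides of the comparison are handled differently.

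**Working it through.** The plan gives no figure on this point, so there is nothing to reproduce. The check is on timing, then on what a shifted baseline does.

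**1. Windows.** The screening examination window is 4 × 7 = 28 days (Section 8.2.1). The exclusion window is 28 days (Baseline definition and Section 12.1.1).

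**2. Transfusion every 28 days or more often.** If no gap between transfusions exceeds 28 days, every hemoglobin lies within 28 days after some transfusion. All screening values fail: 100%, whatever day they are drawn.

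**3. Longer intervals.** Assumptions, not in the documents:
- regular interval of T days;
- last transfusion d = 0 to 28 days before first dose, so Day 1 is rejected;
- screening sample s = 1 to 28 days before first dose;
- all pairs equally weighted;
- a sample on a transfusion day counts as drawn before it.

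There are 29 × 28 = 812 pairs. The sample follows the last transfusion when d > s: 1 + 2 + … + 27 = 378 pairs. Otherwise it fails if the previous transfusion, d + T days before first dose, is at most 28 days earlier than the sample, that is, if s − d ≥ T − 28.

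| T (days) | Fails, last transfusion | Fails, earlier transfusion | Share failing |
|---|---|---|---|
| 35 | 378 | 22 + 21 + … + 1 = 253 | 631/812 = 78% |
| 42 | 378 | 15 + 14 + … + 1 = 120 | 498/812 = 61% |
| 56 | 378 | 1 | 379/812 = 47% |

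Dropping d = 0 gives (378 + 231)/784 = 78%, (378 + 105)/784 = 62% and 378/784 = 48%, so the convention hardly matters.

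**4. Effect on the 1.5 g/dL route.** Let c be the error in baseline, positive if too high. With true change normal with mean μ and standard deviation σ (all assumed), P(response by this route) = 1 − Φ((1.5 + c − μ)/σ).

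| μ, σ (g/dL) | c = −0.5 | c = 0 | c = 0.5 | c = 1.0 | c = 2.0 |
|---|---|---|---|---|---|
| 2.0, 1.0 | 84% | 69% | 50% | 31% | 7% |
| 2.0, 1.5 | 75% | 63% | 50% | 37% | 16% |
| 3.0, 1.0 | 98% | 93% | 84% | 69% | 31% |

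The c = −0.5 column represents a sample drawn at a low point just before a transfusion.

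**5. Who can use the other route.** Assuming 2 units per transfusion, 8 weeks (56 days) contain 56/28 × 2 = 4 units at 28-day intervals and 56/14 × 2 = 8 at 14 days. At 21 days there are 2 or 3 transfusions, so 4 to 6 units. At 35 or 42 days there are 1 or 2 transfusions (2 or 4 units), and at 56 days one (2 units). A subject with exactly 4 units must fall to 4 − 4 = 0. One with fewer than 4 cannot qualify.

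**6. Entry condition.** A clean hemoglobin of 8.0 g/dL fails the condition if raised by 9.0 − 8.0 = 1.0 g/dL. Take 4 responders of 8 (50%) as illustration. Losing one responder from the denominator gives 3/7 = 43%; losing one non-responder gives 4/7 = 57%; counting one responder as a non-responder gives 3/8 = 37.5%, a shift of 12.5 points.

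**The case against.** A reader might infer that erythroid and tri-lineage response are simply biased downward. The documents do not support that.

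- **The transfusion-reduction route.** It does not use the hemoglobin change. At 2 units per transfusion, the subjects whose screening values always fail have at least 4 units in 8 weeks and can qualify this way. This stands as partial protection. It depends on the assumed 2 units, requires complete independence from a subject at exactly 4, and in the Definition of Terms still lies behind the 9.0 g/dL condition.
- **Low values.** RBC transfusion in this plan is tied to hemoglobin of 9.0 g/dL or below, or to symptoms. A screening sample drawn just before a transfusion is likely to be low and would favour response.
- **The denominator.** Subjects lifted to 9.0 g/dL or above may drop out of it or count as non-responders. The plan does not say, so the proportion can move either way.
- **Breach is not inflation.** A sample on day 27 of a 28-day cycle fails the rule yet may carry little transfusion effect.
- **Looser readings of the text.** The 4-week limit is on the screening examination; the screening period itself runs from consent. The closest-value rule may not apply inside the hemoglobin exception. Both points are fair, but neither supplies a transfusion-free condition.
- **Section 12.1.1 may already cover baseline.** Then a frequently transfused subject has a missing baseline rather than an inflated one. Section 12.4 forbids imputation and no rule covers the case, so that reading still needs a repair.

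The endpoints are secondary and Section 12.2 sets no significance level. Section 12.5 leaves a detailed analysis plan to be finalized before database lock. That limits the consequence and shows where the repair can go, but does not remove the gap in the stated rule.

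**Conclusion.** The rule as written can restore the contamination it is meant to remove. For subjects transfused at least every 28 days it always selects a value the plan's own criterion rejects; this follows from the windows alone. The 78%, 61% and 47% for longer intervals rest on regular transfusion and equally likely days. How many subjects are affected is unknown, because the documents do not give transfusion frequency.

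For a sample drawn after transfusion, downward is the likeliest direction through the 1.5 g/dL route. With an assumed mean rise of 2.0 g/dL and SD 1.0, a 1.0 g/dL excess cuts the chance of meeting that criterion from 69% to 31%. Net bias for erythroid or tri-lineage response, in either direction, cannot be derived from the documents. The 12.5-point shift per subject applies only if all 8 in an arm are counted and that subject's classification changes. The point warrants a correction to secondary endpoints; the primary platelet endpoint does not depend on it.

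**What to change.** In the Baseline definition and the analysis plan:

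1. Define the substitute as the most recent pretreatment hemoglobin more than 28 days after any RBC transfusion, including earlier recorded values. Exempt it from the Section 12.1.1 bar on unscheduled measurements, and state that the 28-day rule applies to baseline.
2. If no such value exists, assess erythroid response by the transfusion-reduction route only.
3. As a sensitivity analysis, report the result using the hemoglobin recorded before the most recent transfusion (Section 6.2.3). This should not be the main fallback: for subjects transfused every 28 days or more often it is itself within 28 days of the preceding transfusion, and being a low value it may favour response.
4. Use the same baseline for the 9.0 g/dL condition. State how subjects without a clean value meet that condition and enter the denominator, and reconcile the Definition of Terms with Section 12.1.1.2, which omits it.

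The cost is a few sentences. RBC transfusion dates and pre-transfusion hemoglobin are already on the eCRF from 26 weeks before first dose. The downside is that some subjects will have no hemoglobin-change result, and a clean value may be several weeks old.

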Study duration of each subject in this study is specified as the period from the day of obtaining written informed consent through the end of examinations on completion of treatment (or withdrawal).

Observation and Examination Period

In this study, Week 1 (Day 1) is defined to be the day of initial administration of AMG531. Initial dose evaluation period is defined to be the period from Week 1 to Week 8, Extension period is the period from Week 9 to Week 52, and Long-term treatment period is the period from Week 53 to Week 156.

Aplastic Anemia with Refractory Thrombocytopenia

Aplastic anemia with thrombocytopenia defined as platelet count of $\leq 30 \times 10^9/L$ that does not respond to the immunosuppressive therapy (ATG + cyclosporine), or relapsed after having showed response.

Transfusion Independence

Achieving platelet or RBC transfusion free period of at least 8 consecutive weeks.

Tri-lineage response

Tri-lineage response is defined in those achieving platelet response, erythroid response, and neutrophil response all together.

Normal level

Normal level is defined as platelet counts $>50 \times 10^9/L$, hemoglobin concentration >10.0 g/dL, and neutrophil counts $>1.0 \times 10^9/L$

Stable response

Stable response is defined as platelet counts $\geq 30 \times 10^9/L$, hemoglobin concentration ≥ 9.0 g/dL, and neutrophil counts $\geq 0.5 \times 10^9/L$ maintained during dose tapering or discontinuation without transfusion

Cytogenetic abnormality

Any cytogenetic abnormalities newly emerged during or after the initiation of AMG531 treatment

PROTOCOL SYNOPSIS

I TITLE

A phase 2, Randomized, Open-Label, Parallel, Comparative, Dose-Finding Study to Evaluate the Efficacy and Safety of AMG531 in Aplastic Anemia (AA) Subjects with Thrombocytopenia Refractory to Immunosuppressive Therapy

[figure not shown]
II STUDY OBJECTIVES

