3.3 Study endpoints

3.3.1 Efficacy

3.3.1.1 Primary endpoint

The proportion of subjects achieving a platelet response at Week 9

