3.3.1.2 Secondary endpoints

- The proportion of subjects achieving a platelet response any time during the initial dose evaluation period, Week1 through Week 12, Week 1 through Week 16, Week 1 through Week 24, and Week 1 through Week 52.
- The proportion of subjects who become platelet transfusion independent during the initial dose evaluation period, Week1 through Week 12, Week 1 through Week 16, Week 1 through Week 24, Week 1 through Week 52, Week 1 through Week 104, and Week1 through Week 156
- The proportion of subjects achieving erythroid response and/or neutrophil response during the initial dose evaluation period, Week1 through Week 12, Week 1 through Week 16, Week 1 through Week 24, Week 1 through Week 52, Week 1 through Week 104, and Week1 through Week 156
- Duration of platelet response
- Time to platelet response
- Changes in platelet count, hemoglobin concentration, and neutrophil count as continuous variables
- Changes in bone marrow cellularity and reticulin grade
- Changes in GIMEMA bleeding scale
- The proportion of subjects achieving tri-lineage responses
- The proportion of subjects able to discontinue study drugs after achieving normal level for 8 consecutive weeks without transfusion.
- Duration of study drug discontinuation while maintaining stable response

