6.1.1 Initial-dose evaluation period (Week 1 to Week 8)

AMG531 will be administered at a dose of 1, 3, 6, or 10 µg/kg SC QW for 8 weeks. Dose adjustment (either escalation or reduction) will not be allowed during the initial dose evaluation period except for the cases defined in the 6.1.4 Criteria for discontinuing and resuming study treatment.

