6.1.2 Extension period (Week 9 to Week 52)

Initial dose of AMG531 for the extension period will be decided based on the efficacy and safety data observed during the initial dose evaluation period. If a subject does not show a platelet response at Week 9, the dose will be increased by one level according to Table 6.1.2-1 AMG531 dose adjustment (extension period) table. If no platelet measurement is available due to the platelet transfusion, then that week's platelet response is considered as having no response.

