- 11) Viral serologies for HIV, hepatitis B and C
- 12) 12-lead ECG
- 13) Flow cytometry of the peripheral blood for GPI-cells

8.2.2 Treatment Period: Week 1 (day of initial administration of AMG531) to Week 8

The following observations and examinations during the period of Week 1 (day of initial treatment with AMG531) through to Week 8 will be conducted on the day of study treatment, as a general rule. In consideration of convenience for subjects and investigational sites, \pm 3 days will be allowed except for the subjects assigned to the AMG531 concentration test group. Subjects on dose interruption will also undergo the same observations and examinations. Serum for the determination of AMG531 concentration can be collected at Week 1, Week 4 and Week 8 as described in [Table 8.2.2-1 Schedule for PK sampling](#).

- 1) Vital signs (systolic blood pressure, diastolic blood pressure and pulse rate)
Timing of measurement: Every week before dosing AMG531 in Week 1 to Week 8
- 2) Hematology (WBC, RBC, Hb, Ht, MCV, MCH, MCHC, PLT, Ret and WBC with differential count)
Timing of measurement: Every week before dosing AMG531 in Week 1 to Week 8
- 3) Serum chemistry (TP, ALB, T-Bil, D-Bil, AST, ALT, ALP, LDH, γ -GTP, T-Cho, UA, BUN, Cr, Na, K, Ca, P and Cl)
Timing of measurement: Every week before dosing AMG531 in Week 1 to Week 8
- 4) Blood iron-related parameter (ferritin)
Timing of measurement: Before dosing AMG531 at Week 1 and Week 5
- 5) Blood coagulation (D-dimer)
Timing of measurement: Before dosing AMG531 at Week 1 and Week 5
- 6) Serum AMG531 concentration

Timing of measurement: Before dosing and 4, 12, 24, 48, 72, 96, and 168 hours after dosing AMG531 at Week 1 and Week 8, and before dosing AMG531 at Week 4. Detailed time point with sampling time window is described in Table 8.2.2-1.

7) Serum TPO concentration

Timing of measurement: Before dosing AMG531 at Week 1

8) Antibodies against AMG531 and TPO

Timing of measurement: Before dosing AMG531 at Week 1 (Additional antibody test can be performed on subjects who show clinical findings suggested of possible antibody formation)

9) Cytokine assay

Timing of measurement: Before dosing AMG531 at Week 1

10) GIMEMA bleeding scale (Appendix 3)

Timing of measurement: Before dosing AMG531 at Week 1

Table 8.2.2-1 Schedule for PK sampling

Study Week	Study date	Time of Collection	
Week 1	Day 1	Before dosing of AMG531	within 2 hours
		After dosing of AMG531	4 hours ± 30 minutes
	12 hours ± 90 minutes		

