	24 hours ± 3 hours		
	48 hours ± 3 hours		
	72 hours ± 3 hours		
	Day 2		96 hours ± 3 hours
Day 3		168 hours ± 3 hours	
Day 4			
Day 5			
Day 8 ¹⁾			
Week 4	Day 22	Before dosing of AMG531	within 2 hours
Week 8	Day 50	Before dosing of AMG531	within 2 hours
		After dosing of AMG531	4 hours ± 30 minutes
	12 hours ± 90 minutes		
	24 hours ± 3 hours		
	48 hours ± 3 hours		
	72 hours ± 3 hours		
	Day 51		96 hours ± 3 hours
Day 52		168 hours ± 3 hours	
Day 53			
Day 54			
Day 57 ²⁾			

1) The examination at 168 hours after dosing AMG531 at Week 1 will be conducted before dosing AMG531 at Week 2

2) The examination at 168 hours after dosing AMG531 at Week 8 will be conducted before dosing AMG531 at Week 9

8.2.3 Treatment Period: Week 9 to Week 52

The following observations and examinations during Week 9 through to Week 52 will be conducted on the day of study treatment, as a general rule. In consideration of

convenience for subjects and investigational sites, ± 3 days will be allowed. Subjects on dose interruption will also undergo the same observations and examinations.

- 1) Vital signs (systolic blood pressure, diastolic blood pressure, and pulse rate)
Timing of measurement: Every week before dosing AMG531 at Week 9 through to Week 52
- 2) Hematology (WBC, RBC, Hb, Ht, MCV, MCH, MCHC, PLT, Ret and WBC with differential count)
Timing of measurement: Every week before dosing AMG531 at Week 9 through to Week 52
- 3) Serum chemistry (TP, ALB, T-Bil, D-Bil, AST, ALT, ALP, LDH, γ -GTP, T-Cho, UA, BUN, Cr, Na, K, Ca, P and Cl)
Timing of measurement: Before dosing AMG531 at Week 9, 13, 17, 21, 25, 29, 33, 37, 41, 45 and 49
- 4) Blood iron-related parameter (ferritin)
Timing of measurement: Before dosing AMG531 at Week 9, 13, 17, 21, 25, 29, 33, 37, 41, 45 and 49
- 5) Blood coagulation (D-dimer)
Timing of measurement: Before dosing AMG531 at Week 9, 13, 17, 21, 25, 29, 33, 37, 41, 45 and 49
- 6) Bone marrow biopsy and aspiration with cytogenetics (M/E ratio, cellularity of bone marrow, reticulin grade (reticulin stain/trichrome stain (Appendix 1)), iron stain, narrative pathology report, cytogenetic report and exploratory test described in section 3.3.4).
Timing of measurement: Before dosing AMG531 at Week 25 \pm 2 weeks
- 7) Serum TPO concentration
Timing of measurement: Before dosing AMG531 at Week 9
- 8) Antibodies against AMG531 and TPO

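### The any-time platelet response for the initial period stops at Week 8 and leaves out the Week 9 count that defines the primary endpoint

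*Combined protocol and SAP*

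**What the plan says.** The Definition of Terms (Observation and Examination Period) states: "Initial dose evaluation period is defined to be the period from Week 1 to Week 8". It continues: "Extension period is the period from Week 9 to Week 52". Week 9 therefore belongs to the extension period.

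The primary endpoint (Section 3.3.1.1) is: "The proportion of subjects achieving a platelet response at Week 9". The first secondary endpoint (Section 3.3.1.2) begins: "The proportion of subjects achieving a platelet response any time during the initial dose evaluation period". Its further windows run from Week 1 to Weeks 12, 16, 24 and 52. Section 12.1.1.2 repeats these windows, and the erythroid and neutrophil responses also use the initial period.

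Section 6.1.1 sets the randomized course: "AMG531 will be administered at a dose of 1, 3, 6, or 10 µg/kg SC QW for 8 weeks". The hematology item in Section 8.2.2 reads "Timing of measurement: Every week before dosing AMG531 in Week 1 to Week 8", and its counterpart in Section 8.2.3 reads "Every week before dosing AMG531 at Week 9 through to Week 52". Section 12.1.1 excludes counts from unscheduled visits from the efficacy assessment. Section 6.1.2 then changes the dose: "If a subject does not show a platelet response at Week 9, the dose will be increased by one level".

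**The concern.** A cumulative response rate over the starting-dose period should include every subject who responds at the end of that period. Here it need not. The Week 9 count is the only scheduled count taken after the full randomized course and before any extension dose, and it is the one the any-time window omits. The same subject can then be a success on the primary endpoint and a failure on the secondary endpoint that is meant to be broader.

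The next window does not repair this. Week 1 through Week 12 includes the Week 9 count, but also counts taken after non-responders have moved up a level, so it no longer describes the starting dose. The synopsis objective is to recommend an initial dose, and the initial-period any-time rate is the cumulative measure closest to that purpose.

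**Working it through.** **Inputs.** Weekly dosing in Weeks 1 to 8 (Section 6.1.1); counts before dosing (Sections 8.2.2 and 8.2.3); 8 subjects in each of 4 groups (Section 3.5.1); a ±3-day visit allowance (Section 8.2.3). The stated total reproduces: 4 × 8 = 32. No alpha, power or effect size is given, so no power calculation applies.

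**Calendar.** Nominal day = 7 × (week − 1) + 1. Week 4 gives Day 22 and Week 8 gives Day 50, as in Table 8.2.2-1. Week 9 gives Day 57, the day of the table's 168-hour sample after the Week 8 dose.

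**Doses before each count.** With pre-dose sampling this is week − 1.
- Week 8 count: 7 doses.
- Week 9 count: 8 doses, all before the extension.
- Week 12 count: 11 doses, of which 11 − 8 = 3 are extension doses. For Week 9 non-responders these follow the dose increase.

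**Counts in the window.** Weeks 2 to 8 give 7 counts after the first dose. Running through pre-dose Week 9 gives 8.

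**Effect on a rate.** One subject is 1/8 = 12.5 points. For example, 3/8 = 37.5% (95% CI 8.5 to 75.5) becomes 4/8 = 50.0% (15.7 to 84.3). These are Clopper-Pearson intervals; that method is an assumption, since the plan names none.

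**How often.** The documents give no rate. Let q be the assumed probability that a subject's first response is at Week 9. The chance of at least one among n is 1 − (1 − q)^n, and the expected number is 32q.

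| q | at least one of 8 | at least one of 32 | expected of 32 |
|---|---|---|---|
| 2% | 14.9% | 47.6% | 0.64 |
| 5% | 33.7% | 80.6% | 1.6 |
| 10% | 57.0% | 96.6% | 3.2 |
| 15% | 72.8% | 99.4% | 4.8 |

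**Direction.** The any-time rate minus the Week 9 rate equals the share who respond in Weeks 2 to 8 but not at Week 9, minus the share who first respond at Week 9. It is negative only when the second share is larger. If the window includes Week 9, the second term vanishes and the difference cannot be negative.

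**Why Week 12 is no substitute.** Assume a constant weekly first-response probability h.
- h = 3%: 19.2% (Weeks 2 to 8), 21.6% (Weeks 2 to 9), 28.5% (Weeks 2 to 12).
- h = 5%: 30.2%, 33.7%, 43.1%.
- h = 8%: 44.2%, 48.7%, 60.0%.

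If h doubles after Week 9, the Week 12 figures become 34.9%, 51.6% and 69.6%. These values only illustrate how far the windows can diverge.

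**The case against.** The best counter-argument is that other text ties pre-dose Week 9 data to the initial period. Section 6.1.2 bases the extension dose on initial-period data and then names the Week 9 response. Section 3.5.1 says subjects treated in the initial period are assessed for the primary endpoint, which is at Week 9. Section 2 places the pharmacokinetic assessment in the initial period, yet its last scheduled sample is pre-dose Week 9. This suggests what the authors may have intended, but none of it overrides the definition, and no efficacy rule assigns the Week 9 count to the initial period. Reading Weeks 1 to 8 as Days 1 to 56 does not help: a Week 9 visit on its nominal Day 57 is still outside, while one made on Days 54 to 56 under the visit allowance would fall inside, so inclusion would depend on scheduling.

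It is also fair to say that this is a descriptive secondary endpoint with no significance level (Section 12.2), that time to platelet response is summarized as well, and that Section 12.5 leaves detail to an analysis plan finalized before database lock. All of that stands and limits the consequence.

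Three stronger readings are tempting but not supported:
- A reader might infer that initial-period transfusion independence is impossible, because Day 1 to the Week 8 visit is 50 − 1 = 49 days and 56 are needed. That requires the period to end on Day 50. Eight weeks of treatment with the extension starting at Week 9 reads naturally as Days 1 to 56, and Section 6.2.3 records transfusions by date. The endpoint is then strict (no qualifying transfusion in the period) but attainable.
- A reader might infer that nothing in the plan measures the effect of the full randomized course. The primary endpoint does so, at one time point.
- A reader might put the loss at one responder in eight. That assumes first responses are spread evenly over the Week 2 to Week 9 visits, which no text supports.

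**Conclusion.** The concern holds for the any-time platelet response and, through the same cut-off, for count-based erythroid and neutrophil responses in the initial period. As defined, the window ends after seven of eight randomized doses and can contradict the primary endpoint for the same subject. The size is 12.5 points per affected subject in an arm of 8. The number affected is unknown, and the table rests wholly on assumed values of q. The any-time rate need not fall below the Week 9 rate; it does so only under the condition shown.

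The primary analysis and the sample size do not change. The correction is still worth making because arms are small and the definition is simple to settle in advance. The study is open-label and data are analyzed once all subjects reach Week 17 (Section 12.1), so the boundary should be fixed before those results are seen.

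**What to change.** Add to the Definition of Terms and the analysis plan:
- For any-time platelet response, and for count-based erythroid and neutrophil responses in the initial period, the window is all scheduled assessments after the first dose through the pre-dose Week 9 assessment, before any extension-period dose.
- For platelet transfusion independence and the 8-week transfusion-reduction criterion, the initial-period window is calendar Days 1 to 56 (56 days), based on recorded transfusion dates.

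The two rules should stay separate. A window ending at the Week 9 visit would run from 54 − 1 = 53 to 60 − 1 = 59 elapsed days under the ±3-day allowance, so subjects seen on Days 54 to 56 would fall short of 56 elapsed days. The price of the calendar rule is that after an early Week 9 visit, Days 54 to 56 may include time after the first extension dose.

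The cost is a short text change. All counts and dates are already collected, and no visit, dose or sample size changes.
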